## 8.2 Liposomal doxorubicin

### 8.2.1 Liposomal doxorubicin Toxicity Overview

liposomal doxorubicin is approved for the treatment of patients with multiple myeloma. The toxicity profile has been well described overall. Measures to ensure patients' safety, including the use of stringent inclusions and exclusion criteria, will be taken.

### 8.2.2 Risks Associated with Liposomal doxorubicin

The toxicity profile of Liposomal doxorubicin has been well established and includes the following common toxicities

- **Dermatologic:** Alopecia, Hand-foot syndrome (multiple myeloma, 19% ), Rash (multiple myeloma, 22% )
- **Gastrointestinal:** Constipation (multiple myeloma, 31% ), Diarrhea (multiple myeloma, 46% ), Loss of appetite (multiple myeloma, 19% ), Nausea (multiple myeloma, 48% ), Stomatitis, Vomiting (multiple myeloma, 32% )
- **Neurologic:** Asthenia (multiple myeloma, 22% )
- **Other:** Fatigue (multiple myeloma, 36% ), Fever (multiple myeloma, 31% )

Serious toxicities include the following:

- **Cardiovascular:** Cardiomyopathy, Heart failure (multiple myeloma, 3%)
- **Dermatologic:** Radiation recall syndrome
- **Hematologic:** Anemia (multiple myeloma, 25% ), Myelosuppression, Neutropenia (multiple myeloma, 36% ), Thrombocytopenia (multiple myeloma, 33% )
- **Hepatic:** Hyperbilirubinemia
- **Immunologic:** Anaphylactoid reaction, Infusion reaction

### 8.2.3 Dose Modifications for Liposomal doxorubicin

Prespecified dose modification for Liposomal doxorubicin ( liposomal doxorubicin) guideline for Liposomal doxorubicin will be as shown below:

Dose Level 1: LD 20 mg/m^2

Dose Level 2: LD 30 mg/m^2

Dose Level -1: LD 15 mg/m^2

Dose level -2: LD 10 mg/m^2

A dose of Liposomal doxorubicin below 10 mg/m^2 will not be planned

### 8.2.4 Dose Adjustment Guidelines for Liposomal doxorubicin

**Table 3:** Guideline for the management of Liposomal doxorubicin toxicities

Toxicity and Intensity	Dose Modification
Stomatitis	
Grade 1 (painless ulcers, erythema, or mild soreness)	Redose unless patient has experienced previous Grade 3 or 4 toxicity. If so, delay up to 2 weeks and re-dose at the prior dose
Grade 2 (painful erythema, edema, or ulcers, but can eat)	Delay dosing up to 2 weeks or until resolved to Grade 0-1. If after 2 weeks there is no resolution, Liposomal doxorubicin should be discontinued. If resolved to Grade 0-1 within 2 weeks, and there was no prior Grade 3-4 stomatitis, continue treatment at previous dose. If patient experienced previous Grade 3-4 toxicity, discontinue Liposomal doxorubicin
Grade 3 (painful erythema, edema, or ulcers, and cannot eat) Grade 4 (requires parenteral or enteral support)	Delay dosing up to 2 weeks or until resolved to Grade 0-1. Decrease Liposomal doxorubicin dose by 1 dose level and return to original dose interval. If after 2 weeks there is no resolution, Liposomal doxorubicin should be discontinued.
Hand Food Syndrome HFS (Palmar Plantar Dysesthesias)	
Grade 1 (mild erythema, swelling, or desquamation not interfering with daily activities)	Redose unless patient has experienced previous Grade 3 or 4 HFS. If so, delay up to 2 weeks and decrease DOXIL ® dose by 1 dose level.
Grade 2 (erythema, desquamation, or swelling interfering with, but not precluding normal physical activities; small blisters or ulcerations less than 2 cm in diameter.)	Delay dosing up to 2 weeks or until resolved to Grade 0-1. If after 2 weeks there is no resolution, Liposomal doxorubicin should be discontinued. If resolved to Grade 0-1 within 2 weeks, and there are no prior Grade 3-4 HFS, continue treatment at previous dose and dose interval. If patient experienced previous Grade 3-4 toxicity, continue treatment with a decrease in 1 dose level
Grade 3 (blistering, ulceration, or swelling interfering with walking or normal daily activities; cannot wear regular clothing) Grade 4 (diffuse or local process causing infectious complications, or a bed ridden state or hospitalization)	Delay dosing up to 2 weeks or until resolved to Grade 0-1. Decrease Liposomal doxorubicin by 1 dose level and return to original dose interval. If after 2 weeks there is no resolution, Liposomal doxorubicin should be discontinued.
Neutropenia	
Grade 1, 2, 3	Maintain dose level. Growth factor support is permitted during the phase II portion and the

	phase I after cycle 1.
Grade 4	Hold study treatment until ANC returns to >800/mm  . Reduce Liposomal doxorubicin by 1 dose level. Recommend growth factor support if not already implemented
Febrile Neutropenia	Hold study treatment until patient has stabilized. Dose reduce LD by 1 dose level and recommended growth factor support
Thrombocytopenia	
Grade 1,2,3 without bleeding	Maintain dose level
Grade 4 or grade 3 with clinical bleeding	Delay study treatment until resolved to thrombocytopenia is resolved to grade 3 or less and bleeding stopped. Reduce LD by 1 dose level. Platelet transfusion are allowed per routine clinical care
Serum Bilirubin (when not related to Gilbert's Syndrome)	
1.2 – 3.0 mg/dL	Reduce LD by 25%
> 3 mg/dL	Reduce LD by 50%
Cardiac Toxicities	
Arrhythmia ≥ grade 2	Hold Liposomal doxorubicin until resolved to ≤ grade 1. Decrease Liposomal doxorubicin by 1 dose level
Arrhythmia ≥ grade 3	Discontinue Liposomal doxorubicin. Patients may continue on selinexor if there is a clinical benefit in the opinion of the investigator
Congestive heart failure ≥ grade 2	Discontinue Liposomal doxorubicin. Patients may continue on selinexor if there is a clinical benefit in the opinion of the investigator
Asymptomatic decrease in ejection fraction by 20% or more	Discontinue Liposomal doxorubicin
Other non-hematologic Adverse Events	
Grade 1, 2	Maintain dose level and initiate standard supportive care
Grade 3	Delay dose until resolved to grade 1 or less, then reduce by 1 dose level
Grade 4	Discontinue Liposomal doxorubicin

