Any other drug-related adverse events that may have occurred have resolved to  $\leq$  grade 2 severity.

If these conditions are not met on Day 1 of a new cycle, the subject will be evaluated weekly and a new cycle of treatment will not be initiated until the toxicity has resolved as described above. If study drug dosing was halted during the previous cycle and was restarted with a one-level dose reduction without requiring an interruption for the remainder of the cycle, then that reduced dose level will be initiated on Day 1 of the new cycle. **If study drug dosing was omitted for the remainder of the previous cycle or if the new cycle is delayed due to toxicity newly encountered on the scheduled Day 1**, then the new cycle will be started with a one-level dose reduction of the causative agent.

If recovery from toxicities is prolonged beyond 7 days, then the dose of selinexor, Liposomal doxorubicin or dexamethasone will be decreased by one dose level depending on which agent is felt to be the causative factor or more likely contributing factor.

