#### 6.3.2 Removal of Patients from Treatment

Subjects will be free to discontinue treatment or withdraw from the study at any time, for any reason, or they may be withdrawn/ removed if necessary in order to protect their health (see reasons for withdrawal below). It is understood by all concerned that an excessive rate of withdrawals can render the study uninterpretable; therefore, unnecessary withdrawal of subjects should be avoided.

Patients will be removed from further treatment for the following reasons:

- Disease progression
- Non-compliance with visits and assessment which indicates a potential health hazard to the patient
- Patient no longer consents to participate in the study
- Intercurrent illness that interferes with study assessments
- Incidence or severity of AEs in this study indicates a potential health hazard to the patient
- Investigator discretion

- Pregnancy
- Termination of the study by the sponsor

If there is a medical reason for withdrawal of treatment, the patient will remain under the supervision of the investigator until the AEs have been resolved or declined to baseline values.

In case of premature discontinuation of the study treatment, the investigations scheduled for the EOT should be performed, if possible. Should a patient decide to withdraw, every effort will be made to complete and report the observations as thoroughly as possible. The investigator should contact the patient to determine as completely as possible the reason for the withdrawal. A complete final evaluation at the time of the patient's withdrawal should be made, with an explanation of why the patient is withdrawing from the study. If the reason for removal of a patient from the study is an adverse event or an abnormal laboratory test result, the principal specific event or test will be recorded on the case report form.

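### Table 3's stomatitis rows conflict: after an earlier Grade 3-4 episode, a Grade 2 recurrence that clears within 2 weeks ends liposomal doxorubicin, but a Grade 3-4 recurrence that clears is re-dosed one level lower

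*Combined protocol and SAP*

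**What the plan says.** Section 8.2.4, Table 3, sets LD rules for stomatitis by grade.

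- **Grade 2** (painful, but the patient can eat): dosing waits up to 2 weeks. A patient whose episode clears and who has no earlier Grade 3-4 stomatitis continues at the same dose. For the patient who does have that history: "If patient experienced previous Grade 3-4 toxicity, discontinue Liposomal doxorubicin".
- **Grade 3 or 4** (cannot eat, or needs parenteral or enteral support): dosing also waits up to 2 weeks, then "Decrease Liposomal doxorubicin dose by 1 dose level and return to original dose interval". The row does not mention earlier episodes.
- **Both rows**: "If after 2 weeks there is no resolution, Liposomal doxorubicin should be discontinued".

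The table is titled "Guideline for the management of Liposomal doxorubicin toxicities". Section 8.2.3 lists LD levels of 30, 20, 15 and 10 mg/m² and plans nothing lower. Section 3.1.2 adds a general rule for a cycle delayed by toxicity: "then the new cycle will be started with a one-level dose reduction of the causative agent".

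**The concern.** A dose-modification rule should not become more lenient as the toxicity gets worse. Here it does, for one history. A patient who for a second time could not eat, or needed nutritional support, may receive LD again, while a patient with a milder recurrence may not.

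Section 8.2.2 lists stomatitis among the common LD toxicities. Section 9.2.1 says that selinexor's dose-limiting toxicities are mainly anorexia with poor food and fluid intake. A repeat severe stomatitis therefore adds to the partner drug's main problem. Section 3.1 names three centres, and a table that conflicts with itself invites different LD decisions for the same event.

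**Working it through.** The plan gives no figure to reproduce here, so the check is a trace of the rules followed by simple counts.

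**1. Rules side by side (Table 3), for a patient with an earlier Grade 3-4 episode of the same toxicity**

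| Recurrence | Clears to Grade 0-1 within 2 weeks | Does not clear |
|---|---|---|
| Stomatitis, Grade 2 | LD stopped | LD stopped |
| Stomatitis, Grade 3-4 | LD one level lower | LD stopped |
| Hand-foot syndrome, Grade 2 | LD one level lower | LD stopped |
| Hand-foot syndrome, Grade 3-4 | LD one level lower | LD stopped |

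The conflict sits only in the first column of the stomatitis rows. The hand-foot rows agree with each other.

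**2. Does any other text settle it?**

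- Section 3.1.2 only lowers the causative agent by one level, both for a delayed cycle and in the slow-recovery rule that begins "If recovery from toxicities is prolonged beyond 7 days". Neither adds a stop.
- Table 3's instruction to stop LD at Grade 4 belongs to the block for other non-hematologic events. Stomatitis has its own rows.
- The note about basing changes on the worst preceding toxicity belongs to the selinexor table (section 8.1.4). Carried over to LD, it would point to a reduction after a Grade 2 recurrence, which still contradicts the stop.
- The 10 mg/m² floor does not always block re-dosing. From 20 mg/m², a first Grade 3-4 episode gives 15 and a second gives 10, which is still a planned level. This assumes no other LD reduction and reads the section 3.1.2 cut as the same cut as Table 3's. If the two cuts add up, or LD was already lowered for another reason, the patient can be at 10 before the second episode, with no planned level left.

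**3. Reach**

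Section 1.5.2 says that level 2m is the recommended phase II dose, so dose finding has reported. The Synopsis allows at most 29 − 6 = 23 new phase II patients. The documents give no stomatitis rate. Assumed: 5-15% have a first Grade 3-4 episode, and 10-50% of those have a recurrence of Grade 2 or higher that clears within 2 weeks.

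- Low: 23 × 0.05 × 0.10 = 0.115
- High: 23 × 0.15 × 0.50 = 1.725

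This range of about 0.1 to 1.7 is an upper bound. It still includes Grade 2 recurrences, whose management does not change if a stop is added to the Grade 3-4 row. Phase I patients still on LD would add to it; the documents do not say how many there are.

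**4. Extra LD after a Grade 3-4 rather than a Grade 2 recurrence**

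Take the earliest case: a 20 mg/m² start (level 2m), a first episode after cycle 1 and a recurrence after cycle 2. LD given by then is 20 + 15 = 35 mg/m². A Grade 2 recurrence leaves it there. A Grade 3-4 recurrence continues at 10 mg/m².

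- Treatment of about 3 months (section 3.2): (13 − 1 loading week) / 3 = 4 cycles, so 2 doses remain. Total 35 + 2 × 10 = 55; difference 20 mg/m².
- Same 12 weeks with both delays lasting 2 weeks: cycle 2 at week 5, cycle 3 at week 10, cycle 4 at week 13 and so outside. One dose remains; difference 10 mg/m².
- All 8 cycles: 6 doses remain. Total 35 + 6 × 10 = 95; difference 60 mg/m².
- Later recurrence on the 4-cycle basis: after cycle 3, one dose or 10 mg/m²; after cycle 4, none.

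**The case against.** The strongest objection is that the Grade 3-4 row may be right and the Grade 2 row wrong. The hand-foot Grade 3-4 row is almost the same as the stomatitis Grade 3-4 row and also has no clause on earlier episodes. The hand-foot Grade 2 row, for the same history, reduces by one level. On that comparison the stomatitis Grade 2 stop is the outlier. This stands. A reader might infer that the Grade 3-4 row has plainly lost a stop clause, but the documents do not support that. They show only that the two stomatitis rows do not fit together.

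A second objection is that clinical judgement covers the gap. Re-dosing needs resolution to Grade 0-1 and is at a lower dose, and the table is only a guideline. Section 6.3.2 says "Patients will be removed from further treatment for the following reasons", and the list includes "Incidence or severity of AEs in this study indicates a potential health hazard to the patient" as well as investigator discretion. This lessens the risk but does not repair the rule, because section 6.3.2 takes a patient off treatment in general and is not a stop for LD alone.

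A reader might also fault the Grade 1 row, which returns a patient with an earlier severe episode to the prior dose. That goes too far: the slow-recovery rule in section 3.1.2 may override it when recovery takes more than 7 days.

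**Conclusion.** The inconsistency is certain on the text, within narrow limits: an earlier Grade 3-4 stomatitis and a new episode that clears within 2 weeks. Which row is mistaken is not known.

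The size is very small. The upper bound of 0.1 to 1.7 of at most 23 new phase II patients rests on assumed rates. The extra LD of at most about 20 mg/m² over roughly 4 cycles, or 60 mg/m² over 8, holds for the earliest possible recurrence from a 20 mg/m² start with no other LD reduction. Later recurrence gives less.

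A reader might infer that patients can be re-dosed through repeated severe episodes without limit. The documents do not support this, because nothing below 10 mg/m² is planned. Nor does the point touch the response-rate design: sample size, alpha and power are unchanged. It is a low-priority drafting correction to a safety rule.

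**What to change.** Make the two stomatitis rows agree in the next amendment, after asking the sponsor which was intended.

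- **Default**: add a sentence to the Grade 3-4 row that ends LD if the patient has already had a Grade 3 or 4 stomatitis. This is the safer direction and keeps the Grade 2 stop already written.
- **Alternative**: if the hand-foot approach was intended, change the Grade 2 stop to a one-level reduction.

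Until then, use the regular study call (section 14.3.2) to ask sites to contact the principal investigator before re-dosing LD after a second Grade 3-4 stomatitis.

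The cost is one table cell, carried through the usual principal investigator, company and IRB steps (section 15.1) and put into use at three centres. No visits, data or patients are added. Under the default, a few patients may lose later LD doses: with recurrence after cycle 2, about 2 doses over 4 cycles and at most 6 over 8.

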Grade 1 (ANC < LLN - 1500/mm  ) Grade 2 (ANC < 1500 - 1000/mm  ) Grade 3 (ANC < 1000 - 500/mm  )	Maintain dose level The use of growth factors during selinexor treatment is permitted during the phase II and after cycle 1 is completed in the phase I.
Grade 4 (ANC < 500/mm  )	Hold study treatment until ANC returns to >800/mm  . Dose reduce LD (if appropriate) and consider growth factor support.
Febrile neutropenia, or fever of unknown origin without clinically or microbiologically documented infection (ANC < 1.0 x 10  /L, fever $\geq$ 38.5°C)	Hold study treatment until patient has stabilized. Dose reduce LD (if appropriate) and consider a dose reduction in selinexor
Thrombocytopenia (Platelets) (uncommon)	
Grade 1 (PLT < LLN - 75,000/mm  ) Grade 2 (PLT < 75,000 - 50,000/mm  )	Maintain dose level.
Grade 3 (PLT < 50,000 -25,000/mm  ) without bleeding	Maintain dose level
Grade 4 (PLT < 25,000/mm  ) without bleeding	Delay study treatment until resolved to $\leq$ grade 3. Dose reduce LD (if appropriate) and / or selinexor Platelet transfusions may be given to support platelet levels in patients with clear clinical benefit from selinexor.
Grade $\geq 3$ with bleeding	Delay study treatment until resolved to $\leq$ grade 2, reduce dose by 1 level when resolved.
Hyponatremia (common)	
Grade 1 (Lower Limit of Normal to 130nM)	Maintain dose level, assure adequate fluid, electrolyte and caloric intake, adjust other medications, consider salt supplementation, rule out other causes.
Grade 3 (120-130nM)	Discontinue selinexor until resolved to grade $\leq 1$ then consider reducing dose by 1 level

	especially if another cause is not identified. Check renal function, serum and urinary electrolytes, and rule out other causes.
Diarrhea (uncommon)	
Grade 1 (despite maximal anti-diarrheal medication)	At the first sign of abdominal cramping, loose stools, or onset of diarrhea, it is recommended that the patient be treated according to institutional standard of care. Maintain dose level of selinexor.
Grade 2 (despite maximal anti-diarrheal medication)	Hold therapy. If diarrhea returns as $\geq$ Grade 2, then reduce selinexor dose by one dose level until resolved to $\leq$ grade 1
Grade 3/4 (despite maximal anti-diarrheal medication)	Delay selinexor until resolved to $\leq$ grade 2, then follow guidelines above.
Other adverse events	

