#### **9.2.5 Thrombocytopenia**

The etiology of thrombocytopenia in patients treated with Selinexor is unclear. Selinexor did not cause thrombocytopenia in preclinical toxicology studies (i.e., in animals without prior anticancer therapies), and closely related SINE compounds (i.e., KPT-335) has not caused thrombocytopenia in dogs with newly diagnosed or first relapsed Non-Hodgkin's Lymphoma.

Grade ≥3 thrombocytopenia can be treated with growth factors romiplostim (N-plate®), eltrombopag (Promacta®), rIL-11 (Neumega®) may be used throughout the study.

Dose reduction should then be considered.

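### Tables 2 and 3 set different platelet recovery levels for restarting study treatment after Grade 3 or higher thrombocytopenia with bleeding

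*Combined protocol and SAP*

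**What the plan says.** Two tables deal with thrombocytopenia, and both act on study treatment as a whole rather than on one named drug.

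- Section 8.1.4, Table 2 (selinexor-related toxicities), row for Grade 3 or higher with bleeding: "Delay study treatment until resolved to $\leq$ grade 2, reduce dose by 1 level when resolved". The row does not say which drug is reduced.
- Section 8.2.4, Table 3 (LD toxicities): the row headed "Grade 4 or grade 3 with clinical bleeding" gives the site this instruction: "Delay study treatment until resolved to thrombocytopenia is resolved to grade 3 or less and bleeding stopped. Reduce LD by 1 dose level".

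The tables also word the LD reduction differently after other events.

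- Grade 4 thrombocytopenia without bleeding: Table 2 says "Dose reduce LD (if appropriate) and / or selinexor". Table 3 uses the row quoted above, where the LD cut carries no condition.
- Grade 4 neutropenia: Table 2 says "Dose reduce LD (if appropriate) and consider growth factor support"; Table 3 says "Reduce Liposomal doxorubicin by 1 dose level. Recommend growth factor support if not already implemented".
- Febrile neutropenia: Table 2 again makes the LD cut conditional, and Table 3 again orders one level.

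Section 3.1.2 adds platelet criteria for starting a cycle: above 30,000/mm³ for phase I patients and for phase II patients with Grade 3 thrombocytopenia or neutropenia at baseline, and above 50,000/mm³ for other phase II patients.

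**The concern.** One safety event carries two restart levels, and the protocol does not say which applies. Two sites could follow the text faithfully and treat the same patient differently in the days after a bleed.

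The length of the hold also matters. Under Section 8.1.3, a drug-related delay of more than 4 weeks takes the patient off protocol treatment, and the notes to Table 2 set a similar limit of 28 days. Phase II admits patients with platelets from 30,000/mm³ when marrow plasma cells are at least 50% (Section 4.1, criterion 7b). Such a patient may enter with Grade 3 counts. After a bleed, Table 2 would then require recovery above the patient's own baseline, while Table 3 would not. The choice of table can therefore affect delays, discontinuations and dose intensity in a three-site trial.

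**Working it through.** The plan states no figure to reproduce here. The check sets the rows side by side and converts grades to counts.

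**Inputs.** Table 2 prints Grade 2 as 50,000 to below 75,000/mm³ and Grade 3 as 25,000 to below 50,000/mm³. Table 3 prints no ranges, so Table 2's are used for both. LD is given on day 1 only (Section 7.2.4). At dose level 2m, the recommended phase II dose, selinexor is given on days 1, 8 and 15 (Section 1.5.2).

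**Step 1: restart rules.**

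| Event | Table 2 | Table 3 |
|---|---|---|
| Grade 3 or higher with bleeding | grade 2 or better, i.e. at least 50,000/mm³ | grade 3 or better, i.e. at least 25,000/mm³, and bleeding stopped |
| Grade 4 without bleeding | grade 3 or better | grade 3 or better |

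The tables disagree only in the first row. The ratio of thresholds is 50,000 / 25,000 = 2. The disputed band, once bleeding has stopped, is 25,000 to below 50,000/mm³. A Grade 3 bleed already meets Table 3's platelet condition on the day it occurs, so for that patient only the end of bleeding delays restart under Table 3.

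**Step 2: effect of the day-1 criteria.** On day 1 the lower edge of the band is the larger of 25,000 and the Section 3.1.2 criterion.

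- Under the 30,000 criterion: max(25,000, 30,000) = 30,000, so the dispute runs from above 30,000 to below 50,000/mm³.
- Under the 50,000 criterion: max(25,000, 50,000) = 50,000, so no dispute remains on day 1.
- Selinexor on days 8 and 15: no cycle-start criterion applies, so the full band remains.

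**Step 3: search for a rule of precedence.**

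- Section 3.1.2 directs the reduction to the causative or more likely contributing agent. It sets no recovery grade after a bleed.
- Section 8.1.1 lets the worst grade decide when different toxicities occur together. Here there is one toxicity and one grade.
- The notes to Table 2 base modifications on the worst preceding toxicity, which again gives one grade and two instructions.

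None of these ranks the tables.

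**Step 4: the LD reduction.** From Section 8.2.3, one level from the starting dose is 20 to 15 mg/m², and (20 − 15) / 20 = 25%. After Grade 4 thrombocytopenia without bleeding, Grade 4 neutropenia or febrile neutropenia, Table 2 leaves this cut to judgement and Table 3 requires it.

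**The case against.** The best defence is that each table governs its own drug. Table 2 is titled for selinexor-related toxicity and Table 3 for LD toxicity, and Section 3.1.2 assigns reductions by cause. On that reading, Table 2's conditional LD cut means that LD is reduced if it contributed, and Table 3 says what to do when it did. This has force for the optional-versus-mandatory difference, which is why that point ranks lower.

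It does not settle the restart level. Both bleeding rows hold study treatment, and Table 2 itself directs LD reductions in neighbouring rows. Section 1.5.2 names thrombocytopenia as a potential overlapping toxicity, and the Synopsis (Safety Variables & Analysis) allows an event to be attributed to one or all of the three drugs. Both tables can therefore apply to one bleed.

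A second defence is that Section 3.1.2 already sets day-1 floors. That stands for LD in phase II patients under the 50,000/mm³ criterion, but not for the cases left open in Step 2. Nor are the two instructions strict opposites: a hold to grade 2 with bleeding stopped breaches neither row. But a restart allowed by Table 3 can breach Table 2, and the protocol does not address this.

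A reader might also infer more than the text supports:

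- That the LD cut is optional after a bleed. Table 2's bleeding row names no drug, and its reduction is not conditional.
- That every patient recovering to 25,000–50,000/mm³ is affected. The day-1 criteria exclude some.
- That the 36% neutropenia and 33% thrombocytopenia figures in Section 8.2.2 show how often these rows apply. They carry no grade.
- That an LD cut lasts for all later cycles. The documents give no LD re-escalation rule either way.
- That Section 9.2.5 is a third conflicting rule. Its "Dose reduction should then be considered" is supportive-care advice and does not override a table.

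**Conclusion.** The contradiction on restart after Grade 3 or higher thrombocytopenia with bleeding is real: at least 50,000/mm³ in Table 2 against at least 25,000/mm³ with bleeding stopped in Table 3. It applies in full to selinexor within a cycle, and from above 30,000 to below 50,000/mm³ on day 1 for patients under the lower cycle-start criterion. The unnamed drug in Table 2's bleeding row is a further gap in the same place. The conditional-versus-required LD cut after the three other events is a lesser inconsistency that attribution may partly explain.

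This rests on reading Table 3's grades by Table 2's printed ranges. The documents do not give the frequency of these events, so the number of patients affected cannot be estimated. An effect on the response rate, or a difference between sites, is possible but not shown. Sample size and error rates do not depend on these rows.

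**What to change.** Reconcile Tables 2 and 3 with the cycle-start criteria in Section 3.1.2. For each event discussed here, state one recovery level for study treatment, name the drug for any reduction, and say once whether the LD reduction is mandatory or depends on attribution. The clinical team decides which rule stands.

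The bleeding rows should not be treated as duplicates and one simply deleted: Table 3 names only LD and Table 2 names no drug, so deletion could remove an instruction. The cost is a wording amendment, with no added visits or patients.

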### **4.1 Inclusion Criteria**

Patients must meet all of the following inclusion criteria to be eligible to enroll in this study.

1. Written informed consent in accordance with federal, local, and institutional guidelines
2. Age  $\geq$  18 years
3. Patients with relapsed and refractory multiple myeloma who have received at least 2 prior therapies, which must include lenalidomide and a proteasome inhibitor. Patients must have disease refractory to the most recent therapy. Refractory myeloma is defined as progressive disease during or within 60 days of last therapy. Patients must have previously received or be ineligible for (or refused) autologous stem cell transplant.
4. Patients must have measurable myeloma paraprotein levels in serum ( $\geq$  0.5 g/dL) or urine ( $\geq$  0.2 g excreted in a 24-hour urine collection sample) or by free light chain (involved free light chain greater than 100 mg/L).
5. ECOG performance status of 0-1. ECOG 2 allowed if due to bone disease.
6. Must have an echocardiogram or MUGA indicating LVEF  $\geq$  50% within 42 days prior to first dose of study drug.
7. Adequate hematological function:
  - a. In the phase I portion: absolute neutrophil count (ANC)  $\geq$ 1000/mm^3, platelet count  $\geq$ 50,000/mm^3. GCSF is not allowed during screening or during the first cycle for phase I patients.
  - b. In the phase II portion, if the patient had significant bone marrow involvement (BM plasma cells  $\geq$  50%), a platelet count  $\geq$ 30,000/mm^3 and absolute neutrophil count (ANC)  $\geq$  1000/mm^3 is required. GCSF is allowed during screening and therapy for all phase II patients. Alternatively, with less BM involvement, an ANC  $\geq$  1000/mm^3, and platelet count  $\geq$ 50,000/mm^3 is required.
8. Adequate hepatic function within 14 days prior to loading phase (day -14): total bilirubin  $<$ 2 times the upper limit of normal (ULN) (except patients with Gilbert's

- syndrome who must have a total bilirubin of < 3 times ULN), and alanine aminotransferase (ALT) <2.5 times ULN.
9. Adequate renal function within 14 days prior to loading: measured or estimated creatinine clearance of  $\geq 30$  mL/min, (Cockcroft and Gault)

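### Table 3 gives two liposomal doxorubicin instructions for a grade 3 arrhythmia, its bilirubin percentages can cross the 10 mg/m² floor from a reduced dose, and its use at baseline is left open

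*Combined protocol and SAP*

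**What the plan says.** Table 3 in Section 8.2.4 is titled "Guideline for the management of Liposomal doxorubicin toxicities". Three groups of statements matter here.

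- **Arrhythmia.** The row "Arrhythmia ≥ grade 2" holds LD until recovery to grade 1 or better and then lowers it by one level. The next row, "Arrhythmia ≥ grade 3", discontinues LD.
- **Bilirubin.** Under "Serum Bilirubin (when not related to Gilbert's Syndrome") there are two tiers in absolute units. At 1.2–3.0 mg/dL the instruction is "Reduce LD by 25" per cent; above 3 mg/dL it is "Reduce LD by 50" per cent. The table's other LD reductions move by dose level.
- **Levels and floor.** Section 8.2.3 lists LD at 30, 20, 15 and 10 mg/m² and closes with a limit: "A dose of Liposomal doxorubicin below 10 mg/m"² is not to be planned.

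On entry, inclusion criterion 8 (Section 4.1, and the synopsis) requires total bilirubin below 2 "times the upper limit of normal (ULN) (except patients with Gilbert's" syndrome, for whom the limit is 3 × ULN). Section 7.2.4 gives the LD starting dose as 20 mg/m², with no condition on bilirubin. Section 1.5.2 names dose level 2m, which uses LD 20 mg/m², as the recommended phase II dose (RP2D).

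**The concern.** Two of these are conflicts in the text. The arrhythmia rows prescribe different actions for one event. The percentage cuts can lead to a dose that Section 8.2.3 says is not planned, and nothing says which rule then governs. With three participating centres, the same event could be handled differently by site, for an anthracycline with known cardiac toxicity.

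The third is a gap in scope. A patient without Gilbert's syndrome can meet inclusion criterion 8 with a bilirubin that already lies in the 25% tier. If a site applied the row at cycle 1 day 1, the first LD dose would be below the assigned level. Section 11.3 replaces for the MTD only patients who fail to complete cycle 1 for reasons other than toxicity and without a DLT, so such a patient would still be counted at 20 mg/m². The MTD decision uses 6 patients, and the 6 treated at the RP2D carry over into the 13-patient first stage of phase II (Section 11.2).

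**Working it through.** **The plan's own figures first.** Section 11.2 states 90.7% power at a 40% response rate, a 0.05 significance level at 15%, and an early-stopping probability of 0.058 at 40%. With 13 then 16 patients, continuing on 3 or more responses and succeeding on 8 or more of 29:

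P(success) = Σ over x = 3 to 13 of P[Bin(13, p) = x] × P[Bin(16, p) ≥ 8 − x]

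This gives 0.9069 at p = 0.40 and 0.04999 at p = 0.15. P[Bin(13, 0.40) ≤ 2] = 0.0579. All three agree with the plan. Nothing below changes them.

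**Arrhythmia.** Grade 3 satisfies both the condition of grade 2 or higher and that of grade 3 or higher. The first row leads to resumption one level lower, the second to discontinuation. No assumption is needed.

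**Bilirubin percentages against the LD levels.** Dose after the cut = dose × (1 − cut), for each level in Section 8.2.3:

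| LD dose (mg/m²) | after 25% | after 50% |
|---|---|---|
| 30 | 22.5 (not listed) | 15 |
| 20 | 15 | 10 |
| 15 | 11.25 (not listed) | 7.5 (below 10) |
| 10 | 7.5 (below 10) | 5 (below 10) |

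The floor is crossed only from 15 mg/m² with the 50% cut, or from 10 mg/m² with either cut. That requires the percentage to be taken from an already reduced dose; Table 3 does not say whether its base is the current or the assigned dose. From 20 mg/m² neither cut crosses the floor or leaves the list.

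**Eligibility against the 25% tier.** The documents give no ULN in mg/dL, so it is an assumption. The ranges overlap when 2 × ULN > 1.2, that is, when ULN > 0.6 mg/dL.

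| Assumed ULN (mg/dL) | Eligible below (2 × ULN) | Eligible and in the 25% tier |
|---|---|---|
| 0.8 | 1.6 | 1.2 to below 1.6 |
| 1.0 | 2.0 | 1.2 to below 2.0 |
| 1.2 | 2.4 | 1.2 to below 2.4 |
| 1.3 | 2.6 | 1.2 to below 2.6 |
| 1.5 | 3.0 | 1.2 to below 3.0 |

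For a ULN up to 1.5 mg/dL, no eligible patient without Gilbert's syndrome is in the 50% tier at entry. Read at baseline, the row would therefore give 20 × 0.75 = 15 mg/m².

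**Does the text settle the baseline question?** For the baseline reading: the row uses absolute values, its only exemption is Gilbert's syndrome, and the study calendar draws serum chemistry, including total bilirubin, on cycle 1 day 1. Against it: the table's title concerns toxicities, and Section 7.2.4 attaches no bilirubin condition to the starting dose. The criteria in Section 3.1.2 for starting cycle 1 do not mention bilirubin. The point is neither stated nor excluded.

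**The case against.** The strongest case is that these are wording matters with little reach.

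- **Scope.** A bilirubin measured before the first LD infusion cannot be an LD toxicity. Where the plan wants a lower starting dose for a baseline characteristic it says so, as for dexamethasone by age or prior intolerance (Sections 1.5.2, 7.3.1 and 8.3.3); it has no such text for LD. This carries weight. A reader might infer that some patients counted at the RP2D would start below it. The documents do not support that; they support only that a patient could, if a site applied the row at cycle 1 day 1.
- **Floor.** The limit in Section 8.2.3 may be meant to override any percentage, and a one-level step down from 10 mg/m² meets the same limit. This stands in part, but from 15 mg/m² a one-level step gives 10 while the 50% cut gives 7.5, so the percentages do add a conflict. A reader might also infer that the floor is breached at the RP2D, or that the breach causes a low start. Neither follows: from 20 mg/m² the cuts give 15 and 10. The 22.5 mg/m² case needs LD 30, used only in cohort 4m.
- **Arrhythmia.** Ascending tiers are often read with the more severe row governing. That is a plausible guess at the intent, but the rows do not say it.
- **Effect on results.** A reader might infer bias in the DLT or response results. No count of affected patients is given, so no effect can be computed. Section 8.1.3, written for selinexor, already asks for each dose modification and its reason in the CRF, which lessens the need for a separate flag. It matters, though, that the calendar's footnote 19 keeps serum chemistry out of the eCRF, so bilirubin values would not be there to identify such patients.

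**Conclusion.** The point holds in three limited parts. The arrhythmia rows give incompatible LD instructions at grade 3; this rests on the text alone. The bilirubin percentages conflict with Section 8.2.3 when taken from a reduced dose, giving 7.5 or 5 mg/m² against a floor of 10, and they can also give the unlisted doses 22.5 and 11.25; they do neither from the RP2D dose. The 25% tier overlaps the eligible bilirubin range for any ULN above 0.6 mg/dL (the ULN is an assumption), and the plan leaves open whether the row applies to an eligible baseline value. The most this could do at the RP2D is lower a first dose from 20 to 15 mg/m². The number of patients affected is unknown and probably small. The planned power, significance level and early-stopping probability are unaffected.

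**What to change.** By amendment:

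1. Reconcile the two arrhythmia rows of Table 3 so that each grade meets only one instruction.
2. Reconcile the bilirubin percentages with the LD levels and the floor in Section 8.2.3, including which dose the percentage is taken from and what applies when the result is unlisted or below the floor.
3. Reconcile the bilirubin rows with inclusion criterion 8 (synopsis and Section 4.1) and with the starting dose in Section 7.2.4, by stating whether they apply to an eligible baseline value.

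Which rule to adopt is the investigators' clinical choice. As an option, report any patient whose first LD dose was below the assigned level. The cost is amendment wording and, if the option is taken, one derived variable. Sample size and decision rules do not change.
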